5. TABLE OF EVENTS

Table 3: Table of Events

Assessments	Ref.	Screening Period	Double-blind Treatment Period (DBTP) (Luspatercept or Placebo)						Open-label Period (OLP) (Luspatercept)		Post-treatment Follow-up Period (PTFP)				
		From Week -4 to Day -1	Week 1 Dose 1	From Dose 2 up to Unblinding						Week -1 (Placebo subj. from PTFP) ¹⁶	From Week N Dose 1 (subj. allowed in the OLP) ¹⁷	Subjects who did not complete 48 weeks in DBTP ⁹	All subjects regardless of treatment duration with IP ¹⁰		End of Study ¹¹
		(+3 days)	Day 1 (+3 days)	Day 1 (±3 days)	Dose 6 Day 8 (±3 days)	Dose 6 Day 15 (±3 days)	Weeks ¹⁴ 13, 19, 37, 42 (± 7 days)	Weeks ¹ 24 & 48 (± 7 days)	Week -1 (- 5 days)	Day 1 (+5 days)	Weeks ⁹ 13, 19, 24, 37, 42 & 48 after first dose, if not already done in DBTP (±7 days)	9 wks after last dose (±7 days)	Every 24 wks ¹⁰ (±7 days)	At any time or End of Trial ¹¹	
Informed consent	6.1	X	-	-	-	-	-	-	-	-	-	-	-	-	
Inclusion/exclusion criteria	6.1	X	-	-	-	-	-	X ¹⁶	-	-	-	-	-	-	
Demographics	6.1	X	-	-	-	-	-	-	-	-	-	-	-	-	
Medical history	6.1	X	-	-	-	-	-	-	-	-	-	-	-	-	
β-thalassemia comorbidities assessment for NTDT severity score system	6.1 6.2 6.4	X	-	-	-	-	-	X	-	-	Wks 24 & 48	-	-	-	
β-thalassemia genotype (only if not already available; central or local lab)	6.1	X	-	-	-	-	-	-	-	-	-	-	-	-	
Hepatitis B & C ¹² (local or central lab) if not done within 10 weeks of ICF signature	6.1	X	-	-	-	-	-	X	-	-	-	-	-	-	
Iron Chelation Therapy (history starting from at least 24 weeks prior to Dose 1 Day 1 in DBTP)	6.1 to 6.4	X	Record on ongoing basis, until 9 weeks after last dose ¹⁸												

Table 3: Table of Events (Continued)

Assessments	Ref.	Screening Period	Double-blind Treatment Period (DBTP) (Luspatercept or Placebo)						Open-label Period (OLP) (Luspatercept)		Post-treatment Follow-up Period (PTFP)				
		From Week -4 to Day -1	Week 1 Dose 1	From Dose 2 up to Unblinding						Week -1 (Placebo subj. from PTFP) ¹⁶	From Week N Dose 1 (subj. allowed in the OLP) ¹⁷	Subjects who did not complete 48 weeks in DBTP ⁹	All subjects regardless of treatment duration with IP ¹⁰		End of Study ¹¹
		(+3 days)	Day 1 (+3 days)	Day 1 (±3 days)	Dose 6 Day 8 (±3 days)	Dose 6 Day 15 (±3 days)	Weeks ¹⁴ 13, 19, 37, 42 (± 7 days)	Weeks ¹⁴ 24 & 48 (± 7 days)	Week -1 (- 5 days)	Day 1 (+5 days)	Weeks ^{9,13, 19, 24, 37, 42 & 48 after first dose, if not already done in DBTP (±7 days)}	9 wks after last dose (±7 days)	Every 24 wks ¹⁰ (±7 days)	At any time or End of Trial ¹¹	
Prior / Concomitant / Post treatment (disease specific)/ Medications / Therapies	6.1 to 6.4	X	Record on ongoing basis, until 9 weeks after last dose ¹⁸												
Prior/ Concomitant / Post treatment procedures (eg, surgery, radiation therapy).	6.1 to 6.4	X	Record on ongoing basis, until 9 weeks after last dose ¹⁸												
Transfusion assessment (history starting from at least 24 weeks prior to Dose 1 Day 1 in DBTP and OLTP)	6.1 to 6.4	X	Record on ongoing basis, until 9 weeks after last dose ¹⁸												
Adverse events	6.1 to 6.4	Starting after informed consent signature, on ongoing basis until 9 weeks after last dose, only related SAEs to be reported until End of Study													
Malignancy and premalignancy reporting (Section 10.5.3) ¹³	6.1 to 6.4	Continuous reporting occurrence of any case regardless of causality, starting after informed consent signature										X ¹³	X ¹³		
Vital signs ¹	6.1 to 6.4	X	X	X (every dose)	-	-	-	-	-	X	-	X	-	-	
Height (at Screening only) and weight	6.1 to 6.4	X	X	X (every dose)	-	-	-	-	-	X	-	X	-	-	

Table 3: Table of Events (Continued)

Assessments	Ref.	Screening Period	Double-blind Treatment Period (DBTP) (Luspatercept or Placebo)						Open-label Period (OLP) (Luspatercept)		Post-treatment Follow-up Period (PTFP)				
		From Week -4 to Day -1	Week 1 Dose 1	From Dose 2 up to Unblinding						Week -1 (Placebo subj. from PTFP) ¹⁶	From Week N Dose 1 (subj. allowed in the OLP) ¹⁷	Subjects who did not complete 48 weeks in DBTP ⁹	All subjects regardless of treatment duration with IP ¹⁰		End of Study ¹¹
		(+3 days)	Day 1 (+3 days)	Day 1 (±3 days)	Dose 6 Day 8 (±3 days)	Dose 6 Day 15 (±3 days)	Weeks ¹⁴ 13, 19, 37, 42 (± 7 days)	Weeks ¹ 24 & 48 (± 7 days)	Week -1 (- 5 days)	Day 1 (+5 days)	Weeks ⁹ 13, 19, 24, 37, 42 & 48 after first dose, if not already done in DBTP (±7 days)	9 wks after last dose (±7 days)	Every 24 wks ¹⁰ (±7 days)	At any time or End of Trial ¹¹	
ECOG performance status	6.1 to 6.3	X	-	-	-	-	-	-	X	-	-	-	-	-	
12-Lead electrocardiogram (local reading)	6.1 to 6.4	X	-	-	X	-	-	-	X	-	-	X	-	-	
Echocardiography or MRI (same technique to be used throughout the study): to assess LVEF and TRV	6.1 to 6.4	X, if not done within 8 weeks of ICF signature	-	-	-	-	-	X	X	Wk 144 (± 7 days) if applicable	Wks 24 & 48	-	-	-	
Pregnancy testing ²	6.1 to 6.4	X	X	X (every dose)	-	-	-	-	X (serum, central lab)	X (local lab)	-	X	-	-	
Menstrual status	6.1 to 6.4	X	-	X	-	-	-	-	-	X	-	X	-	-	
Hematology ³ (by central lab Screening, predose Hb value by both local and central lab in DBTP, OLP and PTFP)	6.1 to 6.4	X (at Wk -4 and Wk -3 or Wk -2)	X	X (every dose)	X	X	X	X	X (central lab)	X (local lab and central lab)	X	X	-	-	

Table 3: Table of Events (Continued)

	Ref.	Screening Period	Double-blind Treatment Period (DBTP) (Luspatercept or Placebo)						Open-label Period (OLP) (Luspatercept)		Post-treatment Follow-up Period (PTFP)				
		From Week -4 to Day -1	Week 1 Dose 1	From Dose 2 up to Unblinding						Week -1 (Placebo subj. from PTFP) ¹⁶	From Week N Dose 1 (subj. allowed in the OLP) ¹⁷	Subjects who did not complete 48 weeks in DBTP ⁹	All subjects regardless of treatment duration with IP ¹⁰		End of Study ¹¹
		(+3 days)	Day 1 (+3 days)	Day 1 (±3 days)	Dose 6 Day 8 (±3 days)	Dose 6 Day 15 (±3 days)	Weeks ¹⁴ 13, 19, 37, 42 (± 7 days)	Weeks ¹⁴ 24, 48 & 120 (± 7 days)	Week -1 (- 5 days)	Day 1 (+5 days)	Weeks ^{9,13, 19, 24, 37, 42 & 48 after first dose, if not already done in DBTP (±7 days)}	9 wks after last dose (±7 days)	Every 24 wks ¹⁰ (±7 days)	At any time or End of Trial ¹¹	
Assessments															
Serum Chemistry Panel 1 ⁴ (predose, by central lab up to Week 48/Dose 17)	6.1 to 6.2	X	X	X (every dose up to Dose 17)	-	-	-	-	-	-	-	-	-	-	
Serum chemistry panel 2 ⁴ (predose, by central lab in the DBTP and OLP)	6.1 to 6.4	-	-	X (every 4 doses after Wk 48/ Dose 17)	-	-	-	-	X	X (every 4 doses; central lab)	-	X (central)	-	-	
Urinalysis ⁸ by central lab in the DBTP and local lab in the OLP; Local lab at Screening only if central lab results are not available on time	6.1 to 6.4	X	X	X (every 4 doses from Dose 1: at Dose 5, 9, 13 etc.)	-	-	-	-	X (local lab)	X (every 4 doses from Dose 1: at Dose 5, 9, 13 etc: local lab)	-	X (central)	-	-	

Table 3: Table of Events (Continued)

	Ref.	Screening Period	Double-blind Treatment Period (DBTP) (Luspatercept or Placebo)					Open-label Period (OLP) (Luspatercept)		Post-treatment Follow-up Period (PTFP)				
		From Week -4 to Day -1	Week 1 Dose 1	From Dose 2 up to Unblinding					Week -1 (Placebo subj. from PTFP) ¹⁶	From Week N Dose 1 (subj. allowed in the OLP) ¹⁷	Subjects who did not complete 48 weeks in DBTP ⁹		All subjects regardless of treatment duration with IP ¹⁰	End of Study ¹¹
		(+3 days)	Day 1 (+3 days)	Day 1 (±3 days)	Dose 6 Day 8 (±3 days)	Dose 6 Day 15 (±3 days)	Weeks ¹⁴ 13, 19, 37, 42 (± 7 days)	Weeks ¹⁴ 24, 48 & 120 (± 7 days)	Week -1 (- 5 days)	Day 1 (+5 days)	Weeks ^{9,13, 19, 24, 37, 42 & 48 after first dose, if not already done in DBTP (±7 days)}	9 wks after last dose (±7 days)	Every 24 wks ¹⁰ (±7 days)	At any time or End of Trial ¹¹
Assessments	Ref.													
Serum erythropoietin (EPO), predose, by central lab	6.2 to 6.4	-	X	X (every 4 doses from Dose 1: at Dose 5, 9, 13 etc.)	-	-	-	-	X (every 4 doses from Dose 1: at Dose 5, 9, 13 etc.)	-	X only in DBTP	-	-	
PK (predose on dosing day; serum collection; by central lab)	6.5	-	X	X (Dose 2, 4, and 6, 8, 12, 16 and every 6 doses: at Dose 22, 28, 34 etc.)	X	X	-	-	-	-	-	-	-	
Anti-drug antibody (ADA) ⁵ up to maximum 2 years from Dose 1 Day 1; by central lab	6.6	-	X	X (Dose 2, 4 and 6; 8, 12, 16 and every 6 doses: at Dose 22, 28, 34 etc.)	-	-	-	-	X (if positive in DBTP, every 6 doses) ⁵	-	-	X ⁵	-	

Table 3: Table of Events (Continued)

Assessments	Ref.	Screening Period	Double-blind Treatment Period (DBTP) (Luspatercept or Placebo)						Open-label Period (OLP) (Luspatercept)		Post-treatment Follow-up Period (PTFP)				
		From Week -4 to Day -1	Week 1 Dose 1	From Dose 2 up to Unblinding						Week -1 (Placebo subj. from PTFP) ¹⁶	From Week N Dose 1 (subj. allowed in the OLP) ¹⁷	Subjects who did not complete 48 weeks in DBTP ⁹	All subjects regardless of treatment duration with IP ¹⁰		End of Study ¹¹
		(+3 days)	Day 1 (+3 days)	Day 1 (±3 days)	Dose 6 Day 8 (±3 days)	Dose 6 Day 15 (±3 days)	Weeks ¹⁴ 13, 19, 37, 42 (± 7 days)	Weeks ¹ 24 & 48 (± 7 days)	Week -1 (- 5 days)	Day 1 (+5 days)	Weeks ⁹ 13, 19, 24, 37, 42 & 48 after first dose, if not already done in DBTP (±7 days)	9 wks after last dose (±7 days)	Every 24 wks ¹⁰ (±7 days)	At any time or End of Trial ¹¹	
MRI for LIC (mg/g dw) by T2* or R2 ⁶ as per clinical site's practice	6, 6.1 to 6.4	X, if not done within 12 weeks of ICF signature	-	-	-	-	-	X	X	Wk 144 (± 7 days), if applicable	Wks 24 & 48	-	-	-	
MRI for extramedullary masses ⁶ – only subjects with medical history of masses	6, 6.1 to 6.4	X	-	-	-	-	-	Wk 48	X	Wk 144 (± 7 days), if applicable	Wk 48	-	-	-	
MRI of spleen, if not splenectomized: MRI is the preferred technique for measuring the spleen size ⁶	6, 6.1 to 6.4	X	-	-	-	-	-	X	X	Wk 144 (± 7 days), if applicable	Wks 24 & 48	-	-	-	
Abdominal ultrasound for liver	6, 6.1, 6.3	X	-	-	-	-	-	-	X	-	-	-	-	-	
DXA scan ⁷ – total hip, lumbar spine (read locally)	6, 6.1 to 6.4	X, if not done within 20 weeks of ICF signature	-	-	-	-	-	Wk 48	X	Wk 144 (± 7 days), if applicable	Wk 48	-	-	-	

Table 3: Table of Events (Continued)

Assessments	Ref.	Screening Period	Double-blind Treatment Period (DBTP) (Luspatercept or Placebo)						Open-label Period (OLP) (Luspatercept)		Post-treatment Follow-up Period (PTFP)				
		From Week -4 to Day -1	Week 1 Dose 1	From Dose 2 up to Unblinding						Week -1 (Placebo subj. from PTFP) ¹⁶	From Week N Dose 1 (subj. allowed in the OLP) ¹⁷	Subjects who did not complete 48 weeks in DBTP ⁹	All subjects regardless of treatment duration with IP ¹⁰		End of Study ¹¹
		(+3 days)	Day 1 (+3 days)	Day 1 (±3 days)	Dose 6 Day 8 (±3 days)	Dose 6 Day 15 (±3 days)	Weeks ¹⁴ 13, 19, 37, 42 (± 7 days)	Weeks ¹⁴ 24, 48 & 120 (± 7 days)	Week -1 (- 5 days)	Day 1 (+5 days)	Weeks ⁹ 13, 19, 24, 37, 42 & 48 after first dose, if not already done in DBTP (±7 days)	9 wks after last dose (±7 days)	Every 24 wks ¹⁰ (±7 days)	At any time or End of Trial ¹¹	
6MWT	6.1 to 6.4	X (at wk -4 and between wk -3 and -2)	-	X (every 4 doses, eg, Dose 1, 5, 9, etc.)	-	-	-	X	X	Wk 144 (± 7 days), if applicable	Wks 24 & 48	X	-	-	
QoL questionnaire (NTDT PRO with additional PGI-S item), to be completed as daily diary in the evening	6.1 to 6.3, 6.8	X (daily over 7 days before Dose 1 Day 1)	X	X (daily up to wk 24 and thereafter over 7 days prior to dosing, at every other dose eg, Dose 9, 11, 13, etc.)	-	-	-	-	X (daily over 7 days before Dose 1 Day 1)	X (7 days prior to dosing, at every other dose eg, Dose 9, 11, 13, etc.)	X (over 7 days prior to Wks 13, 24, 37 & 48)	X	-	-	
QoL questionnaires (SF-36v2, FACIT-F and PGI-C) to be completed before knowing the Hb test result on dosing visits	6.1 to 6.3, 6.8	X	X	X (every other dose from Dose 3 and: Dose 5, 7, 9, etc.)	-	-	-	-	X	X (every other dose from Dose 3, 5, 7, 9, etc.)	Wks 13, 24, 37 & 48	X	-	-	

Table 3: Table of Events (Continued)

Assessments	Ref.	Screening Period	Double-blind Treatment Period (DBTP) (Luspatercept or Placebo)						Open-label Period (OLP) (Luspatercept)		Post-treatment Follow-up Period (PTFP)				
		From Week -4 to Day -1	Week 1 Dose 1	From Dose 2 up to Unblinding						Week -1 (Placebo subj. from PTFP) ¹⁶	From Week N Dose 1 (subj. allowed in the OLP) ¹⁷	Subjects who did not complete 48 weeks in DBTP ⁹	All subjects regardless of treatment duration with IP ¹⁰		End of Study ¹¹
		(+3 days)	Day 1 (+3 days)	Day 1 (±3 days)	Dose 6 Day 8 (±3 days)	Dose 6 Day 15 (±3 days)	Weeks ¹⁴ 13, 19, 37, 42 (± 7 days)	Weeks ¹ 24 & 48 (± 7 days)	Week -1 (- 5 days)	Day 1 (+5 days)	Weeks ⁹ 13, 19, 24, 37, 42 & 48 after first dose, if not already done in DBTP (±7 days)	9 wks after last dose (±7 days)	Every 24 wks ¹⁰ (±7 days)	At any time or End of Trial ¹¹	
Healthcare Resource Utilization (HRU)	6.8	Record on ongoing basis, until 9 weeks after last dose ¹⁸													
Serum ferritin (by central lab; also enter in the eCRF all values available in the medical history over 24 weeks prior to Dose 1 Day 1 in DBTP/OLP)	6.1 to 6.4	X	X	X (every dose)	-	-	-	-	X (central)	X (every 4 doses by central)	Wks 24 & 48	X	-	-	
Leg ulcer evaluation (if applicable)	6.1 to 6.4	X	Record on ongoing basis, until 9 weeks after last dose ¹⁸												
Serum GDF11 and other related biomarkers (by central lab; predose sample on dosing days)	6.7	-	X	X (Dose 6, 8, and 16)	X	X	-	-	-	X (every 4 doses)	-	X ¹⁵	-	-	
Hemoglobin fractions (by central lab; predose sample on dosing days)	6.7	X	-	X (every dose)	X	X	-	-	-	X (every 4 doses)	-	X	-	-	
Administer luspatercept / placebo every 21 days and perform drug accountability	6.2 to 6.3, 7.5	-	X	X	-	-	-	-	-	X	-	-	-	-	

ADA = anti-drug (ACE-536) antibody; ALT = alanine aminotransferase; ANC = absolute neutrophil count; AST = aspartate aminotransferase; BMD = bone mineral density; BUN = blood urea nitrogen; DBP = diastolic blood pressure; DBTP = Double-blind Treatment Period; dw = dry weight; DXA = dual-energy x-ray absorptiometry; ECOG = Eastern Cooperative Oncology Group; eCRF = electronic case report form; EPO= Serum erythropoietin; FACIT-F = Functional Assessment of Chronic Illness Therapy-Fatigue; GDF = growth differentiation factor; Hb = hemoglobin; HBsAG = Hepatitis B surface antigen; Hct = hematocrit; Hem = Hematology laboratory assessments; HRU = Health Resource Utilization; ICF = Informed consent form; IP= investigational product; lab = laboratory; LDH = lactic dehydrogenase; LIC= liver iron concentration; LVEF = left ventricular ejection fraction; MCH = Mean corpuscular hemoglobin; MCHC = mean corpuscular hemoglobin concentration; MCV = mean corpuscular volume; MRI = magnetic resonance imaging; 6MWT = 6 minute walk test; NTDT-PRO= Non-transfusion dependent β -thalassemia-patient reported outcome; OLP = Open-label Phase; PGI-C= Patient Global Impression of Change; PGI-S= Patient Global Impression of Severity; PK = Pharmacokinetic; PTFP = Post-treatment Follow-up Period; QOL = quality of life; RBC = red blood cell; RDW = red blood cell distribution width; Ref. = Section Reference; SAE = serious adverse event; SBP = systolic blood pressure; SF-36v2 = Medical Outcomes Study 36-Item Short Form; SGOT = serum glutamic oxaloacetic transaminase; SGPT = serum glutamate pyruvate transaminase; Subj. = subjects; TRV = Tricuspid Regurgitant Velocity; WBC = white blood cell; Wk = week/Week; Wks = weeks.

¹ Vital signs (including heart rate, seated blood pressure [DBP and SBP], and temperature) 2 separate seated blood pressure measurements obtained predose and 10 minutes apart.

² Two pregnancy tests are required during screening for all female subjects of childbearing potential. One test is in serum (beta human chorionic gonadotropin (β -hCG) test with a minimum sensitivity of 25 mIU/mL must be performed within 4 weeks prior Dose 1 Day 1) and the second test can be either in urine or serum within 72 hours of Dose 1 Day 1. During DBTP and OLP, urine or serum pregnancy tests are allowed.

³ Hematology assessment includes RBC count, Hb, Hct, MCV, MCH, MCHC, RDW, WBC count (corrected by erythroblast count) and differential count, absolute neutrophil count (ANC), and absolute lymphocytes count, platelet (all preceding parameters assessed by Central and Local Lab), and reticulocyte absolute values and circulating erythroblasts (nucleated RBC) counts (by Local Lab). On dosing days, hemoglobin levels and WBC count (corrected by erythroblast count) should be measured at predose locally and centrally in the DBTP to ensure the drug administration criteria are met and the modification rules are followed (Section 7.2). **Note:** Hb must be measured by central or local lab in the wk 13, 19, 24, 37, 42, and 48 (\pm 7 days) of DBTP regardless of dose delay and even if the IP is discontinued. Laboratory evaluations may be repeated more frequently if clinically indicated. If the dose is delayed, all planned Day 1 assessments should be performed as detailed in the Table of Events, Table 3, regardless of the dose delays, and appropriate samples sent to the central laboratory. Lab assessments causing the dose delay can be repeated locally until restarting the IP (See Section 6.2.1 for further details).

⁴ Serum chemistry panel 1 (calcium, magnesium, phosphorus, blood urea nitrogen [BUN], creatinine, creatinine clearance, microalbumin, total protein, alkaline phosphatase, bilirubin [total, non conjugated], AST/SGOT, ALT/SGPT, LDH and uric acid) performed by central laboratory up to Dose 17, included. After Dose 17, serum chemistry panel 2 (creatinine, creatinine clearance, alkaline phosphatase, bilirubin [total, non conjugated] AST/SGOT, ALT/SGPT) will be performed every 4 doses by central lab in the DBTP and OLP. In the DBTP, local laboratory results are accepted at screening only if central lab results are not available in timely manner to allow eligibility assessment. Laboratory evaluations can be repeated more frequently, if clinically indicated. If the dose is delayed, all planned Day 1 assessments should be performed as detailed in the Table of Events, Table 3, and appropriate samples sent to the central laboratory, regardless of the dose delays. Lab assessments causing the dose delay can be repeated locally until restarting the IP (See Section 6.2.1 for further details).

⁵ For ADA test, additional blood draws are not needed if a time-matched PK sample will be collected up to maximum 2 years from Dose 1 Day 1 (central lab). The test will be performed using the serum collected for PK samples. In PTFP, ADA samples will be collected every 24 weeks until reaching 2 years from Dose 1 Day 1 of DBTP. After the unblinding, only ADA positive subjects will continue testing for up to 2 years from Dose 1 Day 1 of DBTP, if not already achieved the 2 years of testing. For subjects on placebo in the DBTP, ADA will be tested every 6 doses for up to 2 years from Dose 1 Day 1 of DBTP if ADA positive in the OLP, continue testing in PTFP every 24 weeks up to maximum 2 years from Dose 1 Day 1 of OLP.

⁶ MRI for LIC, extramedullary masses, and spleen should be performed using one MRI acquisition, if possible. MRI for extramedullary masses will be performed at baseline and at Week 48 only to subjects with medical history of masses. MRI of spleen, if not splenectomized: MRI is the preferred technique (same MRI acquisition of LIC, if possible) for measuring the spleen size. Alternatively, ultrasound can be used. Same technique to be used throughout the study.

⁷ DXA scan of the lumbar spine, total hip for bone mineral density (BMD).

⁸ Urinalysis: microalbumin, creatinine, microalbumin/creatinine ratio (morning void; central lab in the DBTP, and local lab in the OLP). In the DBTP, local lab at Screening is accepted only if central lab results are not available on time for eligibility evaluation.

⁹ Subjects who did not complete 48 weeks in DBTP should perform visits at: 9 weeks after last dose and every 24 weeks after last dose up to End of Study, as all subjects regardless of treatment duration with IP, in addition they should perform visits at Weeks 13, 19, 24, 37, 42, and 48 after first dose, if not already done in the DBTP.

- ¹⁰ Regardless of treatment duration with IP, all subjects should perform a visit at 9 weeks after last dose in the DBTP or OLP, and **visits** every 24 weeks at least 5 years from first dose of IP, or 3 years from last dose (whichever occurs later). After the study is unblinded, subjects who discontinue luspatercept in the DBTP may continue the PTFP in the OLP and subsequently in the rollover study.
- ¹¹ End of Study visit should occur after the study is unblinded (ie, 48 weeks after last subject received the first dose of IP), and, at the End of Trial as defined in Section 3.3, whichever occurs later. Or, at the time a subject discontinues from the study.
- ¹² Hepatitis B and C: perform HCV-RNA and HBsAG and/or HBV-DNA by central lab; local lab results are accepted only if central lab results are not available on time for eligibility evaluation.
- ¹³ Subjects are required to see the Investigator at least every 24 weeks to assess for malignancy and premalignancy, as per standard of care.
- ¹⁴ Visits at Weeks 13, 19, 24, 37, 42 and 48 in DBTP should occur only if a dosing visit is not scheduled within ± 7 days of those respective weeks. Week 120 visit might be performed in the DBTP or in the OLP, if applicable (see footnote 17).
- ¹⁵ Serum GDF11 and other related biomarkers sample collection at 9 weeks after last dose to be performed only if not performed at Dose 16, and not performed within the last 12 weeks.
- ¹⁶ Subjects on placebo who discontinued the treatment, but have been assessed as per protocol up to 48 weeks after the first dose of IP, and continued their participation in the PTFP until the time of unblinding, refer to Section 3.1.4, will perform Week -1 visit to re-assess some Inclusion/Exclusion criteria as per Section 3.1.3. Eligibility review/confirmation of selected Inclusion/Exclusion criteria will be performed by the Investigator using local lab data that will be reported in the eCRFs. Note: Week -1 assessments in the OLP can be performed up to pre-Dose 1 Day 1, if needed.
- ¹⁷ All subjects on luspatercept treatment at the time of unblinding, as well as subjects on placebo in the DBTP or in the PTFP at the time of unblinding, if eligible as per Section 3.1.3, can be treated with luspatercept in the OLP starting from Dose 1 Week N (N = number of weeks in the DBTP since Dose 1 Week 1).
- ¹⁸ For early discontinuation subjects, these parameters to be reported up to 48 weeks Post Dose 1 Day 1 or Week 9 post last dose whichever is the later date.

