- Hemoglobin fractions (by central lab; predose sample on dosing days) (as detailed in Section 6.7)
- Administration of luspatercept on Day 1 of each dosing cycle
- QoL Questionnaire (NTDT-PRO with PGI-S for validation): to be completed by the subjects 7 days prior to dosing, every other dose

- QoL Questionnaires (SF-36 v2, FACIT-F, and PGI-C): to be completed by the subjects before knowing the Hb test result on dosing visits indicated in Table 3
- Only at Week 144 post first dose, if applicable, ie, for subjects who entered the OLP prior to reaching Week 144 in the DBTP:
 - Echocardiography or MRI (same technique to be used throughout the study): to assess LVEF and TRV
 - MRI for LIC (mg/g dw) (as detailed in Section 6.1) - only at Week 144 post first dose, if applicable
 - MRI for extramedullary masses - only at Week 144 post first dose, if applicable, only subjects with medical history of masses
 - MRI or abdominal ultrasound for spleen measurement (as detailed in Section 6.1) - only at Week 144 post first dose, if applicable
 - Bone imaging DXA scan (as detailed in Section 6.1) - only at Week 144 post first dose, if applicable
 - 6MWT (6-minute walk test)- only at Week 144 post first dose, if applicable

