6.6. Anti-Luspatercept Antibody

Blood samples will be collected for assessment of anti-drug antibodies (ADAs) against luspatercept in serum in all subjects. At each ADA time point, approximately 3 mL blood will be collected, and serum prepared as described in the study reference guide. However, during the first year of treatment, an additional blood draw is not needed for the ADA test, as the ADA test will be conducted utilizing the PK samples obtained at the same visit. Blood samples for ADA will be taken at the following visits during the study (also see Table 3):

- DBTP: Doses 1 to 16: at predose (Dose 1 Day 1, must be collected before the first dose), Dose 2 Day 1, Dose 4 Day 1, Dose 6 Day 1, Dose 8 Day 1, Dose 12 Day 1, Dose 16 Day 1 and every 6 doses (at Dose 22, 28, 34 etc.) up to maximum 2 years from Dose 1 Day 1)
- OLP: for subjects continuing treatment with luspatercept, only if positive in the DBTP, perform the ADA every 6 doses up to 2 years from Dose 1 Day 1 of the DBTP.
- PTFP: every 24 weeks until the unblinding. After the unblinding, if ADA positive in the DBTP, continue testing every 24 weeks up to maximum 2 years from Dose 1 Day 1 of DBTP. After the unblinding, only ADA positive subjects will continue testing for up to 2 years from Dose 1 Day 1 of DBTP, if not already achieved the 2 years of testing. For subjects on placebo in the DBTP, if ADA positive in the OLP, continue testing every 24 weeks up to maximum 2 years from Dose 1 Day 1 of OLP.

ADA sampling per Investigator's or Sponsor's discretion is allowed and should be recorded as an unscheduled visit.

Detailed procedures of ADA sample collection, processing, and shipping are provided in the study reference guide.

[REDACTED]

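### Protocol Table 3, its footnote 5 and Section 6.6 are not reconciled on ADA testing of placebo subjects who start luspatercept in the OLP, and the footnote's clock leaves late crossovers with no scheduled post-exposure test

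*Protocol*

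**What the plan says.** Three protocol texts bear on ADA sampling of DBTP-placebo subjects once they receive luspatercept.

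- **Section 5, Table 3, ADA row.** The OLP cell reads "X (if positive in DBTP, every 6 doses" and carries superscript 5. The row label sets a limit of "up to maximum 2 years from Dose 1 Day 1; by central lab", without saying which period's Dose 1 is meant.
- **Section 5, Table 3, footnote 5.** Its rule for DBTP-placebo subjects is: "ADA will be tested every 6 doses for up to 2 years from Dose 1 Day 1 of DBTP". The sentence then runs on, without punctuation, to those positive in the OLP, who are to "continue testing in PTFP every 24 weeks up to maximum 2 years from Dose 1 Day 1 of OLP". The general rule just before it is: "After the unblinding, only ADA positive subjects will continue testing for up to 2 years from Dose 1 Day 1 of DBTP".
- **Section 6.6.** "OLP: for subjects continuing treatment with luspatercept, only if positive in the DBTP, perform the ADA every 6 doses". There is no OLP line for crossovers. Under the PTFP, however: "For subjects on placebo in the DBTP, if ADA positive in the OLP, continue testing every 24 weeks", again with the limit counted from OLP Dose 1. The section also permits unscheduled ADA samples at the Investigator's or Sponsor's discretion.

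Section 6.3 lists ADA for OLP subjects only where applicable and points back to Section 6.6.

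**The concern.** For a crossover, a positive result in the DBTP is a result obtained before any luspatercept. Selecting on it, as the Table 3 cell does, therefore says nothing about treatment-emergent antibodies. Section 6.6 makes later follow-up depend on an OLP result that its own OLP bullet never produces. Footnote 5 supplies the test but times it from the start of placebo, whereas the same footnote and Section 6.6 count these subjects' PTFP testing from OLP Dose 1.

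Immunogenicity is a stated safety objective, and Table 2 lists the frequency of anti-drug antibodies and their effect on efficacy and safety as an endpoint. About 50 placebo subjects are planned, so crossovers could be a sizeable newly exposed group beside the roughly 100 randomised to luspatercept. If the subjects with the longest placebo period have no sample, an OLP antibody frequency rests on a subset chosen by enrolment date, or the untested are silently counted as negative.

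**Working it through.** The plan states no figure to reproduce. The check is calendar arithmetic on footnote 5, the most generous of the three texts. I read its positivity condition as belonging to the PTFP clause, as it does in Section 6.6.

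**Inputs**
- Dosing every 21 days (Section 7.2), so OLP Dose n falls 3 × (n − 1) weeks after OLP Dose 1 if no dose is delayed.
- Limit of 2 years from DBTP Dose 1: 2 × 365.25 / 7 = 104.4 weeks.
- OLP of at most 15 months (Section 3.1.3): 15 × 30.4167 / 7 = 65.2 weeks, which holds 22 doses.
- Unblinding 48 weeks after the last subject's first dose (Figure 7 notes). The OLP then awaits primary analysis data and DMC review (Section 3.1.3).
- The text does not say whether the first 6-dose test falls at OLP Dose 6 or Dose 7, so both are shown.

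**Latest OLP entry that still gives one test**
- First test at Dose 6: 104.4 − 15 = Week 89.4.
- First test at Dose 7: 104.4 − 18 = Week 86.4.

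**Scheduled tests before the limit**, counting test times (entry + 15, + 33, + 51 weeks, or entry + 18, + 36, + 54 weeks) up to 104.4:

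| OLP entry (weeks from DBTP Dose 1) | First test at Dose 6 | First test at Dose 7 |
|---|---|---|
| 48 | 3 | 3 |
| 52 | 3 | 2 |
| 60 | 2 | 2 |
| 72 | 1 | 1 |
| 80 | 1 | 1 |
| 86 | 1 | 1 |
| 89 | 1 | 0 |
| 96 and later | 0 | 0 |

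Dose delays push tests later, so these counts are maxima.

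**Entry after Week 104.4.** Footnote 5 has expired. Section 6.6 has no OLP line for these subjects. The Table 3 cell gives nothing, reading the row's limit on the DBTP clock as the footnote does. The PTFP clause cannot start, because it needs a positive OLP result. There is no PK serum to fall back on: the PK row of Table 3 has no OLP samples, and Section 6.5 lists DBTP visits only.

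**Can entry be that late?** Accrual length and the gap g from unblinding to OLP Dose 1 are not given. A subject first dosed a weeks before the last subject enters the OLP at Week 48 + a + g. With g assumed to be 0 to 26 weeks:
- Entry after Week 104.4 needs a > 104.4 − 48 − g, that is 56.4 down to 30.4 weeks.
- No scheduled test needs a > 89.4 − 48 − g, that is 41.4 down to 15.4 weeks (first test at Dose 6), or a > 86.4 − 48 − g, that is 38.4 down to 12.4 weeks (first test at Dose 7).

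The protocol allows for a DBTP of this length. Table 3 footnote 14 has the Week 120 visit falling in either the DBTP or the OLP. DBTP sampling is listed at Dose 34, which is 99 weeks after Dose 1.

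**The case against.** The strongest reply is that there is one rule here, not three rivals. Superscript 5 is attached to the OLP cell, so the footnote qualifies the cell. Section 6.6's bullet is confined to subjects continuing luspatercept, so it is silent on crossovers rather than contrary, and the section refers to Table 3. Read together, crossovers are tested every 6 doses. This largely stands, and it rules out one tempting inference: that antibodies go unmeasured in the whole crossover group. That would follow only from reading the cell without its footnote, or Section 6.6 without Table 3.

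A reader might also infer from "for subjects who entered the OLP prior to reaching Week 144 in the DBTP" in Section 6.3 that placebo subjects are expected to start luspatercept near Week 144. The phrase only sets when an assessment applies, and every earlier entrant satisfies it. With a 65-week OLP, someone entering at about Week 79 (144 − 65) can reach a Week 144 visit. Nor can a percentage untested be given, since it would come wholly from an assumed accrual pattern. The figure of 50 is an upper bound, because entry needs the DMC's agreement and continued participation.

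Three further points stand. Discretionary sampling is available without an amendment. Table 2 marks the immunogenicity endpoint at Weeks 24 and 48, and the SAP covers the double-blind period. Less ADA testing after unblinding is evidently intended for subjects originally on luspatercept.

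What the reply does not meet is the clock. Even on the harmonised reading, the limit runs during placebo and can expire before the first post-exposure test. Ad hoc samples do not give a frequency with a defined denominator.

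**Conclusion.** The three texts need reconciling, and footnote 5 is wrong as written for late crossovers. Under it, a placebo subject entering the OLP after about Week 86 (first test at Dose 7) or Week 89 (first test at Dose 6) has no scheduled post-exposure ADA test. After about Week 104 no text provides one. Earlier entrants have 1 to 3. This assumes 3-weekly dosing without delay and the DBTP clock as footnote 5 states it. How many subjects are affected is unknown.

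The consequence is limited to OLP immunogenicity in the final clinical study report (Section 9.9.2). The primary and key secondary analyses, and the DBTP antibody data for subjects randomised to luspatercept, are untouched. It is worth correcting because the objective is a safety one and the protocol already contains the right anchor.

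**What to change.** State one rule in the Table 3 OLP cell, footnote 5 and Section 6.6: DBTP-placebo subjects who start luspatercept in the OLP are ADA tested every 6 OLP doses regardless of DBTP ADA status, with the 2-year limit counted from Dose 1 Day 1 of the OLP, as it already is for their PTFP testing. Say whether the first such test is at OLP Dose 6 or Dose 7, and exempt these subjects from the positives-only rule after unblinding. Keep the DBTP clock for subjects originally on luspatercept, and name that period in the row label.

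Since 65.2 weeks is less than 104.4, the limit would not bind within the OLP. Every crossover who reaches the first test dose would then have at least one scheduled sample.

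The cost is protocol wording and, over a full OLP, three samples of 3 mL per crossover (Doses 6, 12, 18 or Doses 7, 13, 19) at visits where central-laboratory blood is already drawn. A predose sample at OLP Dose 1 is optional, because DBTP samples taken on placebo already give a pre-exposure result; it would bring the total to four.
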